4.6 EXPLORATORY ENDPOINTS

- Ventilator-free days at day 28
- ICU-free days at day 28
- Hospital-free days at day 60
- Hospital mortality to day 28 and 60

4.7 FOCUSED SAFETY ANALYSIS

The incidence of elevation in plasma COHb $\geq 10\%$ measured on study days 1-3 and pre-specified administration-associated adverse events (**Section 7.1.8**) and serious adverse events (**Section 9.7**).

5 STUDY DESIGN

5.1 OVERALL DESIGN

We will perform a multi-center, prospective, randomized, partially double-blind, placebo-controlled Phase II clinical trial of inhaled CO for the treatment of ARDS. Thirty-two intubated subjects with ARDS will be randomized in a 1:1 ratio to receive inhaled CO versus inhaled air placebo for up to 90 minutes daily for a total of 3 days. Subjects randomized to receive iCO will be administered 200 ppm CO to achieve a COHb level of 5-8%.

5.2 SCIENTIFIC RATIONALE FOR STUDY DESIGN

We have designed our study to optimally balance risks and potential benefits of iCO treatment, recognizing that we are still early in the developmental pathway. We chose a partially double-blind design so that there would always be an unblinded assessment of COHb levels in order not to exceed potentially toxic thresholds. The 1:1 randomization between iCO and placebo will provide us the maximum statistical power to identify both any adverse effects and any potential beneficial outcomes in our critically ill study population.

5.3 JUSTIFICATION FOR DOSE

Subjects randomized to CO will be administered iCO daily at 200 ppm for up to 90 minutes for three consecutive days. The rationale for fixed 200 ppm dosing is based on our Phase I trial demonstrating safety and the ability to achieve COHb levels which do not exceed 8%, a level which has been shown to be safe in prior human studies^{45,111,114,115,117,118,132}, and protective in animal models of sepsis and ALI^{34-36,38,40,42,43,48,55-65}. Although direct exposure of lung epithelial cells to CO gas at low levels may evoke local cytoprotective effects, it is unlikely that systemic effects will be achieved without elevation of tissue CO levels, for which COHb is a surrogate. Prior studies have demonstrated safety of iCO at 500-1000 ppm in humans¹¹⁵, a dose associated with reduced inflammation in NHPs⁶⁴, therefore we do not anticipate epithelial toxicity at a dose of 200 ppm.

The rationale for three consecutive days of treatment is based on our prior work in healthy individuals demonstrating safety and activation of mitochondrial biogenesis after CO inhalation at 200 ppm for 1 hour/day for 5 consecutive days^{6,45}. The rationale for once-daily dosing as opposed to continuous inhalation, as with inhaled nitric oxide (NO) or other inhaled pulmonary vasodilators, is based on pre-clinical studies showing that iCO treatment for short periods of time induces transcriptional programs of mitochondrial biogenesis^{45,46,50,51,133} and induces autophagy^{43,49,50,134-136} leading to downstream protection without the need for continuous CO inhalation. In addition, once-daily iCO dosing will optimize subject safety by ensuring that COHb levels do not exceed our target range of 5-8%, and that CO accumulation will not occur as treatments are separated by 4-6 half-lives for CO elimination¹³⁷⁻¹³⁹.

5.4 END OF STUDY DEFINITION

A participant is considered to have completed the study if he or she has completed all phases of the study including the six month telephone neurocognitive assessment as shown in the **Time-Events Schedule, Section 1.3**.

6 STUDY POPULATION

6.1 INCLUSION CRITERIA

All intubated patients ≥ 18 years old with ARDS according to the Berlin criteria¹⁵ will be eligible for inclusion. Subjects will be recruited from the medical, surgical, cardiac, and burn ICUs at each center with a specific focus on patients with ARDS secondary to infection, trauma, transfusion, burns, hemorrhagic shock, inhalation, and/or oxygen exposure.

1. ARDS is defined when all four of the following criteria are met:
 - a. A $\text{PaO}_2/\text{FiO}_2$ ratio ≤ 300 with at least 5 cm H_2O positive end-expiratory airway pressure (PEEP)
 - b. Bilateral opacities on frontal chest radiograph (not fully explained by effusions, lobar/lung collapse, or nodules) within 1 week of a known clinical insult or new or worsening respiratory symptoms
 - c. A need for positive pressure ventilation by an endotracheal or tracheal tube
 - d. Respiratory failure not fully explained by cardiac failure or fluid overload; need objective assessment (e.g., echocardiography) to exclude hydrostatic edema if no risk factor present
(Appendix C)
2. ARDS onset is defined as the time the last of criteria 1-4 are met. ARDS must persist through the enrollment time window of 168 hours.

6.2 EXCLUSION CRITERIA

An individual who meets any of the following criteria will be excluded from participation in this study:

1. Age less than 18 years
2. Greater than 168 hours since ARDS onset
3. Pregnant or breastfeeding
4. Prisoner
5. Patient, surrogate, or physician not committed to full support (exception: a patient will not be excluded if he/she would receive all supportive care except for attempts at resuscitation from cardiac arrest)
6. No consent/inability to obtain consent or appropriate legal representative not available
7. Physician refusal to allow enrollment in the trial
8. Moribund patient not expected to survive 24 hours
9. No arterial or central line/no intent to place an arterial or central line
10. No intent/unwillingness to follow lung protective ventilation strategy
11. Severe hypoxemia defined as $\text{SpO}_2 < 95$ or $\text{PaO}_2 < 90$ on $\text{FiO}_2 \geq 0.9$
12. Hemoglobin < 7.0 g/dL
13. Subjects who are Jehovah's Witnesses or are otherwise unable or unwilling to receive blood transfusions during hospitalization
14. Acute myocardial infarction (MI) or acute coronary syndrome (ACS) within the last 90 days
15. Coronary artery bypass graft (CABG) surgery within 30 days

16. Angina pectoris or use of nitrates with activities of daily living
17. Cardiopulmonary disease classified as NYHA class IV
18. Stroke (ischemic or hemorrhagic) within the prior 1 month, cardiac arrest requiring CPR within the prior 72 hours, or inability to assess mental status following cardiac arrest
19. Burns > 40% total body surface area (TBSA)
20. Severe airway inhalational injury
21. Use of high frequency oscillatory ventilation
22. Use of extracorporeal membrane oxygenation (ECMO)
23. Concomitant use of inhaled pulmonary vasodilator therapy (eg. nitric oxide [NO] or prostaglandins)
24. Diffuse alveolar hemorrhage from vasculitis
25. Concurrent participation in other investigational drug study

Reasons for Exclusions:

Patients less than 18 years of age are excluded because the participating ICUs do not typically admit pediatric patients and we believe the benefit/risk ratio for children to receive iCO is not appropriate at this early stage. Patients with ARDS for more than 168 hours are excluded in order to evaluate more clearly the effects of iCO early in the course of lung injury. Patients with severe hypoxemia or need for ECMO are excluded because they may not have adequate reserve to tolerate the reduction in oxygen carrying capacity. The parameters of $\text{SpO}_2 < 95$ or $\text{PaO}_2 < 90$ on $\text{FiO}_2 \geq 0.9$ are used rather than a simpler $\text{PaO}_2/\text{FiO}_2$ ratio of 100 to define severe hypoxemia for both enrollment and daily treatment to better account for factors affecting arterial oxygen content and to ensure an additional safety margin during treatment of enrolled subjects. These criteria exclude patients with $\text{PaO}_2/\text{FiO}_2 \leq 100$ (PaO_2 90/ FiO_2 0.9), but also explicitly specify a safety margin of 0.1 for FiO_2 . These criteria are currently approved by the Institutional Review Boards (IRBs) at our participating clinical centers, our DSMB, and the FDA for our Phase I CO ARDS trial (NCT02425579).

Patients with hemoglobin < 7.0 g/dL, Jehovah's witnesses, or patients otherwise unable or unwilling to receive blood transfusions during hospitalization are excluded because of the volume of blood drawn for monitoring during iCO therapy may place these patients at greater risks from complications of anemia. Moribund patients and patients with extensive body surface area burns have a high incidence of AEs and lactic acidosis that will confound the safety assessment. Pregnancy, recent stroke, or cardiac arrest are exclusions because iCO may reduce oxygen delivery to the fetus and recently injured brain respectively. Patients with alveolar hemorrhage from vasculitis are excluded because the mechanism of lung injury is different from ARDS and diffuse alveolar damage. Patients with acute MI within 90 days, recent CABG, and angina pectoris are excluded because of a potential excess risk of reducing oxygen delivery to the myocardium. Patients with congestive heart failure and NYHA class IV cardiopulmonary disease are excluded because of concerns about ventricular arrhythmias and high mortality. Patients ventilated with high frequency oscillatory ventilation are excluded because administration of iCO with this mode of ventilation may be potentially unreliable. Patients on ECMO are also excluded because the effects of CO uptake and elimination from the blood during ECMO are unknown. Patients on concurrent inhaled pulmonary vasodilator therapy are excluded as these inhaled medications may interfere with the dosing of iCO.

Patients who are cigarette smokers, but otherwise eligible for inclusion, will not be excluded from potential enrollment in the study. Rather, enrolled subjects will be screened with daily COHb levels and study drug treatment held if $\text{COHb} \geq 3\%$. This criterion was implemented for our Phase I trial and this Phase II trial as smoking history obtained from surrogate decision makers may be unreliable and the average COHb half life is

240 minutes when breathing room air and less on supplemental oxygen¹³⁷⁻¹³⁹. Since current smoking rates amongst military (24%)¹⁴⁰ and veteran populations (20%)¹⁴¹ are higher than for civilians (15%)¹⁴², exclusion on the basis of smoking history would preclude many patients from receiving this potentially beneficial treatment. Instead, this protocol incorporates treatment holds on the basis of daily COHb levels, which will allow otherwise eligible patients to be treated safely and have the opportunity to benefit from this potentially new promising therapy. We anticipate enrolling smokers at a frequency similar to their proportion in our target populations.

6.3 STUDY INITIATION TIME WINDOW

All ARDS criteria must occur concurrently within the same 24 hour period. The onset of ARDS is when the last criterion is met. Patients must be enrolled within 168 hours of ARDS onset. Information for determining when these time window criteria were met may come from either the site hospital or a referring hospital reports. Following randomization, the low tidal volume protocol for mechanical ventilation must be initiated within two hours.

The first treatment of study drug should be given within 24 hours of randomization. The day of randomization will be considered study day zero.

6.4 SCREEN FAILURES

Screen failures are defined as participants who consent to participate in the clinical trial but are not subsequently randomly assigned to the study intervention or entered in the study. A minimal set of screen failure information is required to ensure transparent reporting of screen failure participants, to meet the Consolidated Standards of Reporting Trials (CONSORT) publishing requirements and to respond to queries from regulatory authorities. Minimal information includes demography, screen failure details, eligibility criteria, and any SAE.

Individuals who do not meet the criteria for participation in this trial (screen failure) because of severe hypoxemia (Exclusion Criterion 11), low hemoglobin (Exclusion Criterion 12), use of high frequency oscillatory ventilation (Exclusion Criterion 21), or use of inhaled pulmonary vasodilators (Exclusion Criterion 22) may be rescreened. Rescreened participants will be assigned the same participant number as for the initial screening.

6.5 STRATEGIES FOR RECRUITMENT AND RETENTION

One hundred inpatient subjects will be recruited for this study at seven enrolling medical centers. Subjects will be identified by prospective medical record review. We anticipate that the distribution of gender, race, and ethnicity of the subjects enrolled will be similar to the demographic characteristics of ICU patients admitted to each of our participating centers and be proportional to the enrollment distribution. No gender, race, and/or ethnicity group will be excluded from participation in our proposed study.

Study coordinators at each site will screen inpatient ICUs daily to identify all potential subjects based on the pre-defined inclusion and exclusion criteria. The recruitment process will consist of electronic medical record (EMR) review of all intubated patients in the ICUs at each site to determine if a potential subject meets study eligibility criteria. EMR alerts will also be used to assist research coordinators in the early identification of potential participants that meet study eligibility criteria. The research coordinators at each site will identify potential participants and review the study eligibility criteria in detail with the site PI or designee. No recruitment or advertisement materials will be utilized to recruit patients, however flyers will be posted in ICU staff areas to educate colleagues and other health care providers about study eligibility criteria and the importance of participation in clinical research. We will also engage the ICU clinical communities through

conferences and other educational resources at each site as our ICU colleagues will play a critical role in the recruitment, retention, and overall conduct of the clinical trial.

Participants will be hospitalized in the ICU at the time of informed consent and throughout the treatment period of the study protocol, thus we do not foresee difficulties in adherence with the study drug treatment. For participants who are extubated prior to completion of the 3 day treatment portion of the protocol, all data will be analyzed on a modified intention-to-treat (MITT) basis. For long-term follow-up outcomes, we will use web-based investigator tools for messaging and scheduling reminders to contact participants.

Several engagement strategies will be adopted to ensure retention of study participants for assessment of long-term outcomes following hospitalization. First, we have designed the study protocol to minimize participant burden in order to optimize subject retention in the trial. We have designed the protocol such that the long-term follow up requires no travel or costs and entails three brief (2-5 minute) telephone calls at day 28, day 60, and 6 months. Second, we have established an efficient tracking system for long-term follow-up. At the time of consent, participants and/or their legally authorized representative (LAR) will be asked to provide email addresses and several phone numbers (home, work, cell) and to indicate the best times to contact them and whether voice and/or text messages can be left.

As many ICU patients are discharged to long-term care facilities following hospitalization, we will consent study participants for permission to contact them at a long-term care facility if applicable. The names and contact information of up to three people who can be contacted for assistance with locating participants will also be requested. Written informed consent to contact these individuals will be obtained, including a description of the scope of the information to be obtained (eg. forwarding addresses versus questions about the clinical status of the participant). In the event of being unable to contact study subjects, we will send letters and/or emails to participants who are unresponsive to personal contact. We will also obtain consent to use social security numbers to determine vital status of participants lost to follow-up.

To mitigate retention risks at the time of consent, we will educate subjects (and their LARs) about their important role as research participants, the requirements of the study, and clearly orient participants to the study demands, tasks, and responsibilities.

Most of the patients approached for participation in this research protocol will have limitations of decision-making abilities due to their critical illness or need for sedating medications. Hence, most patients will not be able to provide informed consent and accordingly, informed consent will be sought from the potential subject's LAR. For subjects for whom consent was initially obtained from a surrogate, but who subsequently regain decision-making capacity while in hospital, we will obtain formal written consent for continuing participation, inclusive of continuance of data acquisition. The initial consent form signed by the surrogate will reflect that such continuing consent will be obtained when possible. All patients who recover decision-making capacity will also be approached for written re-consent for genetic testing. Subjects will not be compensated for participation in the study.

6.5.1 SCREENING

Federal regulations at 45 CFR 46(a)(3) require the equitable selection of subjects. The ICUs will be screened to determine if any patient meets the inclusion and exclusion criteria. Data that have been collected as part of the routine management of the patient will be reviewed to determine eligibility. No protocol-specific tests or procedures will be performed as part of the screening process. If any patient meets criteria for study enrollment, then the attending physician will be asked for permission to approach the patient or his/her surrogate for

informed consent. Justifications of exclusion criteria are given in **Section 6.2**. These exclusion criteria neither unjustly exclude classes of individuals from participation in the research nor unjustly include classes of individuals from participation in the research. Hence, the recruitment of subjects conforms to the principle of distributive justice.

A screening log will be kept to track subjects that could potentially meet inclusion criteria. All patients meeting the inclusion criteria will be entered into the StudyTRAX database. If the patient is not enrolled, information explaining why enrollment did not occur will be entered into StudyTRAX (exclusion criteria, attending physician denial, patient refusal, etc. see **Appendix D** for a listing of the de-identified data to be collected on screened, non-enrolled subjects).

6.5.2 JUSTIFICATION OF INCLUDING VULNERABLE SUBJECTS

The present research aims to evaluate the safety and efficacy of iCO as a treatment for patients with ARDS who are intubated and mechanically ventilated. Due to the nature of this illness, the vast majority of these patients will have impaired decision-making capabilities. This study cannot be conducted if enrollment is limited to only those subjects with decision-making capacity. Potential benefits to participation in this study are increased survival and ventilator free days (VFDs).

7 STUDY INTERVENTION

[figure not shown]

Figure 10. Schema of CO Delivery System and ventilator.

of the ventilator and inlet port of the humidifier. The gas sampling line will be placed between the outlet port of the humidifier and the patient wye as shown. The study drug will be administered by an RT and a physician study staff member OR a physician study staff member alone. A physician study staff member will be present at the bedside during and immediately available for an additional 90 minutes after administration of the study drug for any clinical concerns that arise. The administering RT and physician study staff member OR the physician study staff member alone will be unblinded to the treatment assignments and will conceal the gas cylinders and COventDS to assure that the study coordinator and treating ICU team remain blinded to the study drug assignment. A physician investigator will be at the bedside of the study subject during and immediately available after the administration of the study drug for an additional 90 minutes to provide any necessary emergency care in conjunction with the patient's clinical ICU team.

7.1 STUDY INTERVENTION(S) ADMINISTRATION

7.1.1 CO DELIVERY SYSTEM

Inhaled CO or placebo air will be administered to mechanically ventilated subjects using a mechanical ventilator approved for NO delivery and the CO Delivery System developed by 12th Man Technologies (**Figure 3, Appendix A**). See **Appendix A** for details of the CO Delivery Device testing, assembly, calibration, and standard operating procedures (SOP). The CO Delivery System will be calibrated and connected to the ventilator (**Figure 10**) as described in **Appendix A**. As per the SOP and illustrated in the schema in **Figure 10**, the injector module will be connected between the inspiration port

7.1.2 CO OR PLACEBO CYLINDERS

The gas cylinders proposed for this clinical trial are AG aluminum cylinders with a CGA 500 valve and will be supplied by Praxair. The cylinder contains approximately 360 liters of 5000 ppm (0.5%) CO in room air (21% oxygen) and poses no increased flammability risk. Placebo tanks will contain medical grade air. The gas cylinder's nominal size is 5 inches in diameter by 17 inches tall. Given the flow limitation from the regulator of ~7 liters per minute and a minimum of 6 air exchanges per hour in an average 15x15x10 ICU room, we do not expect ambient CO levels to exceed the OSHA permissible exposure limit (PEL) of 50 ppm as an 8 hour time-weighted average. We measured ambient CO levels during our animal studies using the COventDS and were unable to detect increases in ambient CO levels throughout assembly, calibration, and delivery of CO to the animals. In addition, we simulated CO administration with an ICU ventilator (Puritan-Bennett 840), CO Delivery System, and lung model in an ICU room at Massachusetts General Hospital at 500 ppm for over 2 hours and ambient CO levels were near zero and well below the OSHA PEL.

7.1.3 DOSING AND ADMINISTRATION

Subjects will be treated with inhaled CO at a dose of 200 ppm or placebo. Placebo will consist of medical-grade air in identical appearing aluminum AG gas cylinders.

The study drug will be administered for up to 90 minutes daily for three days following randomization or until discontinuation of mechanical ventilation, whichever occurs first. For patients who have a tracheostomy, the equivalent of extubation for the purposes of this protocol will be breathing via tracheostomy with unassisted breathing.

7.1.4 CO MONITORING

The study drug concentration will be monitored continuously with the COventDS built-in analyzer to assure that the accurate dose is delivered. A physician investigator will assess subjects prior to daily iCO treatment. Subjects will have blood drawn daily for measurement of COHb and lactate prior to study drug administration. If COHb \geq 3% (assessed by unblinded physician) or lactate \geq 4 mmol/L, the study drug will be held and the subject will be reassessed for treatment the following day. An electrocardiogram (EKG) will also be performed daily prior to study drug administration to evaluate for cardiac exclusion criteria. Blood COHb levels will be measured with an IL GEM Premier Co-oximeter and SpCO measured with a noninvasive pulse oximeter (Masimo Radical-7).

Blood (arterial or venous) will also be drawn at 20, 60, 75, 90, and 180 minutes for safety monitoring of COHb levels. If an arterial line is not available, venous blood will be used for COHb monitoring as we⁴⁸ and others¹⁴³⁻¹⁴⁵ have shown that venous levels are as accurate and reliable as arterial measurements. Blood (arterial or venous) will also be drawn for blood gas analysis (using the local clinical lab) at 90 minutes or at the completion of treatment, if discontinued sooner than 90 minutes. If arterial blood is not available and venous blood gas is used, PaO₂/FiO₂ will be estimated using the formula $SpO_2/FiO_2 = 64 + 0.84 \times PaO_2/FiO_2$, as long as SpO₂ \leq 97% and subject remains intubated as described in the Statistical Analysis Plan.

The unblinded physician will review and adjudicate COHb measurements and communicate any study drug treatment holds to the administering study staff. COHb levels will be entered into the electronic case report forms (eCRFs) in a separate limited-access project in StudyTRAX by the unblinded RT or physician. The study drug will be administered for up to 90 minutes daily for up to 3 days following randomization or until discontinuation of mechanical ventilation, whichever occurs first.

The concentration of the study drug will be measured by the built-in gas monitor in the COventDS. The CO Delivery System contains an inhaled gas monitor, which is an electrochemical device that monitors the inhaled gas for concentrations of CO (0-800 ppm) and O₂ (15-100%) to assure that safe levels are inhaled. The sample pump maintains a constant flow of gas to the sensors. Samples of inspired gases are taken with a continuous ~400 mL/min sample pump just proximal to the patient's airway to reflect actual inspired gases. Alarms will sound on high or low CO or O₂ concentrations.

Ambient air CO concentrations will be measured in real time with a Dräger Pac 7000 CO detector to assure that ambient levels are maintained within the recommended limits for occupational exposure of a maximum of 50 ppm. Ambient air CO detectors will be calibrated every 6 months per the manufacturer's instructions to ensure proper functioning.

All CO monitoring will be carried out by the administering RT and physician study staff member OR physician study staff member alone and concealed from the study coordinator and clinical team. The physician study staff member will be responsible for maintaining a separate password-protected limited-access project within the database with the subject identification number and CO-related measurements (SpCO, COHb, ambient CO) which the study coordinator will not have access to.

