- b) Worst creatinine (or urine output), bilirubin, and platelet count for that date
- c) Worst Glasgow Coma Scale for that date
- d) Vasopressor use and maximal dose for that date

Glasgow Coma Scale (GCS): The GCS is a determination of the best eye opening, motor, and verbal responses at any given time. The GCS is documented by the clinical team as part of routine ICU nursing assessment. If not available, the GCS will be assessed by the study staff as described in **Appendix E4**.

Richmond Agitation Scale (RASS): RASS is a scale used to measure the agitation or sedation level of a patient. RASS scoring is documented by the clinical team as part of routine ICU nursing assessment. If not available, the RASS will be assessed by the study staff as described in **Appendix E5**.

Blood gas analysis: The following values will be recorded from the arterial blood gas (ABG) results: pH, PCO₂, PO₂, and base excess or deficit. ABG is required for baseline assessment. If no ABG is available on subsequent days, record blood gas analysis results from the venous blood gas (VBG).

ScvO₂: ScvO₂ will be recorded if available.

Vasopressors and Inotropes Review: The following vasopressors/inotropes will be recorded in the study eCRFs. (epinephrine, norepinephrine, phenylephrine, vasopressin, dopamine, dobutamine, phosphodiesterase inhibitors, including dose).

Fluid Intake/Output: Fluid intake and output (most recent 24 hour value) or mean hourly value for most recently available period. Diuretic administration will also be recorded if applicable.

Renal replacement therapy status: Renal replacement therapy status within the last 24 hours will be recorded.

Concomitant Medications Review: The following medications will be recorded in the study eCRFs: aspirin,

angiotensin converting enzyme inhibitors (ACEIs), steroids, neuromuscular blockade, inhaled NO or prostaglandins.

Microbiological Results: Microbiological results will be recorded in the eCRF when ordered for clinical purposes.

- a) Blood cultures
- b) Urine cultures
- c) Sputum cultures
- d) BAL cultures
- e) CSF cultures if available
- f) Stool
- g) Other

Vital Status: Vital status will be assessed at Days 28, 60, and 6 months. Subjects who have been discharged from the hospital will be contacted by phone. Additional information will be collected on discharge status, ventilator status, and vasopressor status at Days 28 and 60.

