9.3.2 VENTILATOR PROCEDURES

FiO₂ will be increased prior to study drug administration in order to achieve a PaO₂ ≥ 80 or SpO₂ ≥ 95%. Ventilator management, including weaning, will follow the modified ARDS Network lower tidal volume (6 mL/kg PBW) protocol (**Appendix G**)⁹. If not already being utilized, this low tidal volume protocol for mechanical ventilation must be initiated within two hours of randomization. Since the time a patient achieves unassisted ventilation affects a secondary endpoint, VFDs, and because recent evidence-based consensus recommendations have identified a best practice for weaning, weaning strategy will also be controlled by protocol rules in accordance with these evidence-based recommendations. This newer weaning strategy is a simplified version of the protocolized weaning strategy used in prior ARDS Network studies (**Appendix G**). Study drug administration will be continued in patients undergoing weaning from mechanical ventilation as in **Appendix G** unless the subject is deemed ready for extubation by the clinical team.

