9.5.1 REVIEW PARAMETERS PRIOR TO ADMINISTRATION OF STUDY DRUG

Review the Daily Hold Parameters (detailed information in **Section 7.1.6**). Administration of the study drug will be held if the following criteria are met.

Daily Hold Parameters:

- COHb level $\geq 3\%$
- Lactate ≥ 4 mmol/L
- ST elevation MI or unstable angina/non ST elevation MI concerning for ACS
- Unstable atrial or ventricular arrhythmia
- Severe hypoxemia defined as SpO₂ < 95 or PaO₂ < 90 on FiO₂ ≥ 0.9
- Hemoglobin < 7.0 g/dL
- Diffuse alveolar hemorrhage from vasculitis
- Use of high frequency ventilation
- Use of inhaled pulmonary vasodilator therapy (eg. NO or prostaglandins)
- Use of ECMO
- Occurrence of an AE meeting criteria for study drug hold or discontinuation (**Sections 7.1.6, 7.1.8.**).

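### When only a venous gas exists, the SpO2-based substitute for PaO2/FiO2 is biased low at high FiO2 and can create a false fall from the arterial baseline

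*Combined protocol and SAP*

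**What the plan says.** Section 7.1.4 gives the linear rule for one situation: "If arterial blood is not available and venous blood gas is used". Its only conditions are SpO2 at or below "97% and subject remains intubated as described in the Statistical Analysis Plan". No range of FiO2 is attached to it.

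Four other parts of the protocol bear on how the rule behaves:

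- **Baseline and later days.** Section 9.1 (Blood gas analysis) states "ABG is required for baseline assessment" and lets a venous gas stand in on later days when no arterial one is available. The Time-Events Schedule in 1.3 agrees.
- **Oxygenation before dosing.** In 9.3.2, FiO2 "will be increased prior to study drug administration in order to achieve a" PaO2 of at least 80 or SpO2 of at least 95%.
- **Hold rule.** Section 9.5.1 lists "Severe hypoxemia defined as SpO₂ < 95 or PaO₂ < 90 on FiO₂ ≥ 0.9" among the daily hold parameters. Section 6.2 uses the same limits for exclusion and, in its reasons, links PaO2 90 on FiO2 0.9 to a ratio of 100.
- **Endpoint and model.** PaO2/FiO2 on days 1-5 and 7 is a secondary endpoint (4.5). Section 10.4.3 analyses it by repeated-measures ANCOVA on treatment, time and their interaction, adjusted for baseline and ARDS severity. No term or sensitivity analysis for the measurement method is described.

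**The concern.** At a given saturation the oxyhemoglobin curve fixes PaO2 without reference to FiO2. The linear rule does not respect this: at constant SpO2, the PaO2 it implies falls steadily as FiO2 rises. Dosing at high FiO2 is not barred. Section 9.5.2 gives instructions for FiO2 above 55%, and the hold at FiO2 ≥0.9 applies only when an oxygenation limit is missed. Central access without an arterial line is enough for entry (6.2, criterion 9), so venous-only sampling is foreseen by the design.

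The method can therefore change within one patient, from a measured arterial ratio at baseline to an imputed one later. If FiO2 is high at that point, the series shows a deterioration that reflects the formula and not the lung.

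**Working it through.** **Inputs.** The line and the SpO2 cap of 97% come from 7.1.4; PaO2 90, SpO2 95 and FiO2 0.9 from 6.2 and 9.5.1; PaO2 80 and SpO2 95% from 9.3.2.

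**1. The protocol's own figure.** 90 / 0.9 = 100, as 6.2 has it.

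**2. The inverted rule.** PaO2/FiO2 = (SpO2/FiO2 − 64) / 0.84. Multiplying by FiO2, implied PaO2 = (SpO2 − 64 × FiO2) / 0.84. Each 0.1 rise in FiO2 at fixed SpO2 lowers the implied PaO2 by 6.4 / 0.84 = 7.6 mm Hg.

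**3. At FiO2 0.9.**
- SpO2 95%: (105.56 − 64) / 0.84 = 49.5, an implied PaO2 of 44.5.
- SpO2 97%: (107.78 − 64) / 0.84 = 52.1, the most the rule can return there.
- A patient with SpO2 ≥95 and PaO2 ≥90 on FiO2 0.9 has a ratio of at least 100.
- Run forward, a ratio of 100 needs SpO2/FiO2 = 64 + 84 = 148, so SpO2 = 148 × 0.9 = 133%, which is impossible.

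**4. Across FiO2, at SpO2 95%, against PaO2 80.**

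| FiO2 | Rule | 80/FiO2 | Difference |
|---|---|---|---|
| 0.3 | 300.8 | 266.7 | +13% |
| 0.4 | 206.5 | 200.0 | +3% |
| 0.5 | 150.0 | 160.0 | −6% |
| 0.6 | 112.3 | 133.3 | −16% |
| 0.7 | 85.4 | 114.3 | −25% |
| 0.8 | 65.2 | 100.0 | −35% |
| 0.9 | 49.5 | 88.9 | −44% |
| 1.0 | 36.9 | 80.0 | −54% |

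**5. Sensitivity to the comparator.** The documents do not state which PaO2 goes with SpO2 95%. A standard dissociation curve (an assumption) gives 75.7 mm Hg. At FiO2 0.9 that is 75.7 / 0.9 = 84.1, and the rule is 41% low. At FiO2 0.7 it is 108.1, and the rule is 21% low. The direction holds for 75.7, 80 or 90.

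**6. The false fall.** Take a patient with PaO2 90 on FiO2 0.9 at baseline (ratio 100) whose gas exchange does not change, and whose next gas is venous with SpO2 95 to 97%. The recorded ratio becomes 49.5 to 52.1, an apparent loss of about 48 to 51 mm Hg. With PaO2 80 on FiO2 0.7 and SpO2 95%, it goes from 114.3 to 85.4, a loss of about 29. At FiO2 0.4 to 0.5 little happens.

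**The case against.** The strongest reply has five parts.

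**The thresholds are not pairs.** SpO2 95 is set beside PaO2 90 in one place and PaO2 80 in another, joined by *or* each time. A reader might infer that the rule returns half of a value the protocol itself assigns to SpO2 95%. The documents state no such equivalence. This stands. The statement about FiO2 0.9 needs no equivalence, however: it concerns a patient who meets both limits.

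**Several conditions must coincide.** The gas must be venous only, FiO2 high, SpO2 at most 97% and the patient intubated. Arterial gas is the first choice, and a patient whose arterial line is removed may well be on a lower FiO2, where the rule does well. This stands as a limit on frequency, which the documents do not give.

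**Both arms share the rule.** A reader might infer a biased treatment effect, or set the error against the 81 mm Hg detectable difference in Table 5. Neither is supported. The error belongs to single readings, whereas Table 5 concerns a Day 7 difference between arm means. Bias between arms needs a difference in FiO2 or venous-gas use.

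**Spill-over and CO effects are not established.** LIS, SOFA and OI use PaO2 or its ratio, but the supplied text does not say that the substitute enters them. Table 3 might suggest that CO lowers SpO2 in one arm only. It reports oxyhemoglobin in healthy volunteers, not pulse-oximeter readings, and nothing says that the 90-minute gas supplies the daily endpoint.

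**The equation is published for ARDS, and the SAP may say more.** The cited source and separate SAP text were not available here, so a limit on FiO2 may exist. That does not cure 7.1.4, which states the rule without one.

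**Conclusion.** The point holds for high FiO2. There the substitute is too low: at most 52.1 at FiO2 0.9 under the SpO2 cap, where a patient meeting both limits has at least 100. Against PaO2 80 at SpO2 95% it is about 25% low at FiO2 0.7, 44% at 0.9 and 54% at 1.0. It is adequate at 0.4 to 0.5.

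The consequence is added noise and distorted time trends in a secondary endpoint, because measured baseline values are compared with imputed later ones. No bias between arms has been shown, and the trial-level effect cannot be sized without the FiO2 distribution and the frequency of venous-only gases.

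The conclusion assumes that the rule in 7.1.4, which appears beside the 90-minute gas, also supplies the daily PaO2/FiO2 values when no arterial gas exists. It is the only substitute that the supplied text gives.

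**What to change.** In 7.1.4 and the SAP:

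1. Replace the linear back-calculation, at every FiO2, with PaO2 imputed from SpO2 (≤97%) by a named non-linear oxyhemoglobin dissociation equation, divided by the recorded FiO2. A single method throughout avoids a jump where two methods would meet.
2. Flag each value as arterial or imputed.
3. Wherever a substitute PaO2 is used in LIS, SOFA or OI, use this same imputed value.
4. Add a sensitivity analysis of PaO2/FiO2 restricted to arterial values.

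The cost is a change of wording and a little more analysis work; SpO2 and FiO2 are already collected, and patient care is unaffected. Imputed values will still carry error, because small differences in SpO2 near 97% correspond to sizeable differences in PaO2. The arterial-only analysis will have fewer observations.
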